#### **3.5.3. Vital Signs**

Supine blood pressure and pulse measurements will be taken at all time points listed in the Schedule of Activities given in the protocol.

The baseline measurement is the pre-dose measurement at Hour 0 taken on Day 1. The maximum decrease and increase from baseline over all measurements taken postdose for supine systolic and diastolic blood pressures will be determined. The maximum increase from baseline will be calculated by first subtracting the baseline value from each postdose measurement to give the change from baseline. The maximum of these values over the entire study will then be selected, except in the case where a subject does not show an increase. In such an instance, the minimum decrease should be taken.

Similarly, the maximum decrease from baseline will be determined by selecting the minimum value of the changes from baseline. In cases where a subject does not show a decrease, the minimum increase should be taken.

#### **3.5.4. ECG**

Single supine 12-lead ECG will be taken at all time points listed in the Schedule of Activities given in the protocol. The baseline measurement is the pre-dose measurement at Hour 0 taken on Day 1.

The QT, QTc, PR, QRS and heart rate will be recorded at each assessment time.

If not supplied, QTcF will be derived using Fridericia's heart rate correction formula:

$$QTcF = QT/(RR)^{1/3} \quad \text{where } RR = 60/HR \text{ (if not provided)}$$

The maximum absolute value (post-dose) and the maximum increase from baseline for QTcF, QT, heart rate, PR and QRS, will be determined for all measurements taken post-dose for QTcF, heart rate, PR and QRS.

The maximum increase from baseline will be calculated by first subtracting the baseline value from each postdose measurement to give the change from baseline. The maximum of these values over the entire study will then be selected, except in the case where a subject does not show an increase. In such an instance, the minimum decrease should be taken.

#### **3.5.5. Other Safety Data**

Additional safety data will be collected as described in the protocol and will be listed if collected in the sponsor's database.

### **4. ANALYSIS SETS (POPULATIONS FOR ANALYSIS)**

Data for all participants will be assessed to determine if participants meet the criteria for inclusion in each analysis population prior to unblinding and releasing the database and classifications will be documented per standard operating procedures.

Population	Description
Enrolled	All participants who sign the ICD.
Randomly assigned to investigational product	All participants who sign the ICD and meet all eligibility criteria.
Evaluable	The PK concentration population is defined as all participants enrolled and treated who have at least 1 concentration measurement of ritlecitinib. The PD population is defined as all enrolled and treated who have at least 1 TO measurement.
Safety Analysis Set	All participants who take at least 1 dose of investigational product.

## 5. GENERAL METHODOLOGY AND CONVENTIONS

### 5.1. Hypotheses and Decision Rules

No formal hypothesis testing will be performed in this study.

### 5.2. General Methods

Descriptive analyses will be performed. Some measures will be summarized using graphical representations by dose, where appropriate.

#### 5.2.1. Analyses for Continuous Endpoints

For continuous variables, the data will be summarized using the number of subjects, mean, median, standard deviation, minimum, and maximum in accordance with current Pfizer's data and reporting standards. For appropriate PK parameters, geometric mean and geometric coefficient of variation (geocv%) will also be summarized. For the summaries of TO and baseline corrected TO, the 90% CI for the mean will also be presented.

Summaries will be presented by dose and nominal time post-dose, if appropriate.

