8.4.2. Pharmacodynamics

The following samples for pharmacodynamics are required and will be collected from all participants in this study as specified in the [SoA](#):

- Target occupancy blood sample.

CCI

8.4.2.1. Target Occupancy:

Whole blood samples (approximately 30 mL) will be collected according to the timepoints specified in the [SoA](#) in sodium heparin tubes. PBMCs will be lysed and protein will be isolated. An ATP-competitive probe will be used to pull-down kinases that are not covalently bound to PF-06651600. Protein isolate will be digested with trypsin and unique peptides within JAK3, BMX, BTK, ITK, TEC and TXK have been identified and will be used to quantitate the amount of each kinase that is not occupied by ritlecitinib.

CCI

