9.3.1. Primary Endpoints

The primary endpoint in human PBMCs is TO of JAK3, BTK, ITK, RLK, TEC and BMX after a single dose of ritlecitinib. Target occupancy for each kinase at time t will be evaluated as follows:

$$\% \text{ Target Occupancy}_t = 100 \% - \% \text{ Free Target}_t$$

with TO_0 as the baseline variable of target occupancy, which is the mean of the two pre-dose measurements at Hour -1 and Hour 0 on Day 1. If only one of the two pre-dose measurements is available, TO_0 is the available pre-dose measurement.

TO profiles will be assessed graphically and summarized by nominal timepoints using descriptive statistics.

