### 3.4. Baseline Variables

Baseline TO, CCI will be defined as the mean of the two pre-dose measurements at Hour -1 and Hour 0 on Day 1. If only one of the two pre-dose measurements is available, the baseline will be defined as the available pre-dose measurement.

In general, for all other analyses, baseline will be defined based on observations collected prior to first dose. Baseline values for demographics, medical and other history will be based on measures collected at Visit 1/Screening visit. Study Day 1 is defined as the day the subject receives first dose of study drug. For purposes of all other analyses including analyses for change from baseline, the baseline value will be defined as measured on Day 1 pre-dose. If a value is missing on Day 1, then the last available observation before Day 1 will be used.

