## **6. ANALYSES AND SUMMARIES**

### **6.1. Primary Endpoint(s)**

The primary analysis will be performed on the PD population (see [Section 4](#)).

The primary endpoint is TO of JAK3, BTK, ITK, RLK, TEC and BMX after a single dose of ritlecitinib. TO profiles, CFB and percent CFB in TO profiles of each kinase will be assessed graphically and summarized by dose and nominal timepoints using appropriate descriptive statistics as described in [Section 5.2.1](#).

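### Change and percent change from baseline in percent TO are redundant, not computable or misleading, because pre-dose occupancy should be about zero and the reference for % Free Target is not stated

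*SAP*

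**What the plan says.** - **Assay.** Protocol 8.4.2.1 says that the peptides "will be used to quantitate the amount of each kinase that is not occupied by ritlecitinib". It describes measuring unoccupied kinase only and names no 100% reference.
- **Endpoint.** Protocol 9.3.1: "Target occupancy for each kinase at time t will be evaluated as follows", followed by %TO_t = 100% - %Free Target_t, "with TO_0 as the baseline variable of target occupancy". SAP 3.1 repeats this. TO_0 is the mean of the Hour -1 and Hour 0 values but does not enter the formula. SAP 3.4 lets it rest on one sample: "If only one of the two pre-dose measurements is available, the baseline will be defined as the available pre-dose measurement".
- **Protocol analysis.** Protocol 9.3.1: "TO profiles will be assessed graphically and summarized by nominal timepoints using descriptive statistics".
- **SAP analysis.** SAP 6.1, under the primary endpoint: "TO profiles, CFB and percent CFB in TO profiles of each kinase will be assessed graphically and summarized by dose and nominal timepoints".
- **Interval.** SAP 5.2.1: "For the summaries of TO and baseline corrected TO, the 90% CI for the mean will also be presented". It does not link the second term to CFB, to percent CFB or to anything else.
- **Meaning of CFB.** SAP 3.5.3 spells it out for vital signs, and 3.5.4 does the same for ECG: "first subtracting the baseline value from each postdose measurement to give the change from baseline". No separate rule is given for TO.

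**The concern.** CFB and percent CFB suit a variable with a meaningful, non-zero starting level. Percent TO before the first dose has none: nobody has drug on board, so the true value is nil and any measured departure is assay offset or noise. Subtracting that departure moves the ceiling of the scale from 100 to a different value for each participant. Dividing by it gives figures with no interpretation.

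The ceiling matters here. Protocol 2.1 reports about 100% occupancy of JAK3 and most TEC kinases at early times in the mouse model, so some of the key human values may lie near 100. If offsets differ between kinases, the CFB tables would also show differences between JAK3 and the TEC kinases that come from the assay.

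**Working it through.** The documents give no SD, precision or power figure for TO, so there is no planned figure to reproduce. The check is algebra, plus a simulation under stated assumptions.

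**1. True pre-dose occupancy.** This is a single-dose study. Exclusion criterion 14 bars known participation in a ritlecitinib trial within 30 days of dosing. Protocol 2.1 gives kinase half-lives of 2-3 hours (JAK3, ITK) and 12-24 hours (BTK). Thirty days is 720 hours, or 720/24 = 30 half-lives at the slowest of these. None is given for RLK, TEC or BMX, but nothing suggests carry-over.

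**2. Formulas.**
- CFB = TO_t - TO_0
- Percent CFB = 100 x (TO_t - TO_0) / TO_0
- Ratio form = 100 x (1 - Free_t/Free_0) = 100 x (TO_t - TO_0) / (100 - TO_0)

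**3. If % Free is scaled to the participant's own pre-dose mean.** TO_0 = 0, CFB = TO_t, and percent CFB divides by zero.

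**4. If it is scaled to anything else.** At a measured TO_t of 100 (illustrative TO_0):

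| TO_0 | CFB | Percent CFB | Ratio form |
|---|---|---|---|
| -20 | 120 | -600 | 100 |
| -10 | 110 | -1100 | 100 |
| -5 | 105 | -2100 | 100 |
| 5 | 95 | 1900 | 100 |
| 10 | 90 | 900 | 100 |
| 20 | 80 | 400 | 100 |

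**5. Baseline noise in the interval.** The number per arm, n = 8, is from Protocol 4.1. The following are assumed: true baseline 0, independent errors, pre-dose SD per sample of 5, 10 or 20 points, and the level and SD of TO_t. With two pre-dose samples, SD(CFB) = sqrt(SD_t^2 + s^2/2). For SD_t = 1 and s = 10 this is sqrt(1 + 50) = 7.1. With one pre-dose sample it is sqrt(1 + 100) = 10.0. Mean 90% CI half-widths over 100,000 simulated arms:

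| TO_t (SD) | Pre-dose SD | Raw TO | CFB | Ratio form |
|---|---|---|---|---|
| 99 (1) | 5 | 0.65 | 2.4 | 0.65 |
| 99 (1) | 10 | 0.65 | 4.6 | 0.65 |
| 99 (1) | 20 | 0.65 | 9.2 | 0.67 |
| 50 (10) | 10 | 6.5 | 7.9 | 6.9 |

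In the three rows with TO_t at 99, mean CFB exceeds 100 in 22%, 35% and 42% of arms. For percent CFB with pre-dose SD 10, the 5th to 95th percentiles of the arm mean run from about -11,400 to +11,100.

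**6. Which correction is right depends on the error.** Three illustrative cases with TO_0 = 15 or -15:

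| Source of TO_0 | True occupancy | Raw TO | CFB | Ratio form |
|---|---|---|---|---|
| Shared scale factor (Free_0 = 85) | 50 | 57.5 | 42.5 | 50 |
| Pre-dose noise only (true 100, measured 85) | 50 | 50 | 35 | 41.2 |
| Additive background of 15 (Free_0 = 115, Free_t = 15) | 100 | 85 | 100 | 87 |

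**The case against.** A reader might infer that the SAP defines baseline-corrected TO as a difference, and that the primary result is therefore biased. The documents support neither step. The term is undefined, and the protocol's amendment history records that similar wording was deleted from 9.3.1, so the SAP phrase may be a leftover. The primary endpoint is uncorrected TO, which has its own summaries and its own 90% CI and contains no baseline term. No formal comparison of JAK3 with the TEC kinases is planned.

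Two further objections also stand. First, no passage gives an error model. Subtraction is right for an additive background (100 against 87 for the ratio), and under pure pre-dose noise raw TO beats both corrections. Second, the ratio has a cost: at mid-range occupancy it is slightly less precise than raw TO (6.9 against 6.5). Near full recovery it can be noisier than CFB: at true occupancy 0 with the pre-dose value measured as 85, CFB is -15 and the ratio is 100 x (1 - 100/85) = -17.6.

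These points narrow the concern without removing it. SAP 6.1 plans CFB and percent CFB by name, whatever baseline corrected TO means. Percent CFB fails under every reading of % Free Target. CFB adds nothing under one reading and depends on an unstated error model under the others.

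**Conclusion.** The point holds for the baseline-related TO summaries only. With TO_0 = 0, CFB is a duplicate and percent CFB does not exist. With TO_0 non-zero, CFB misses 100 by exactly TO_0 when measured TO is 100, and percent CFB runs to hundreds or thousands with a sign set by the baseline error. Near saturation the CFB interval is mostly baseline noise: a half-width of 2.4 to 9.2 points against about 0.65 for raw TO, for assumed pre-dose SDs of 5 to 20.

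This rests on true pre-dose occupancy being about zero, which the design supports, and on CFB meaning subtraction for TO as it does elsewhere in the SAP. The sizes of TO_0, the SDs and the TO levels are assumptions. The preference for the ratio assumes a multiplicative offset. That is the natural choice when the assay quantifies unoccupied kinase and the participant's own pre-dose amount represents 100%, but the documents do not establish it. The analyses are descriptive (SAP 5.1, Protocol 9.5), so what is at stake is the readability of the tables and intervals; no error rate is affected.

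**What to change.** 1. In Protocol 9.3.1 and SAP 3.1, state what % Free Target is a percentage of.
2. In SAP 5.2.1 and 6.1, define baseline-corrected TO as 100 x (1 - Free_t / mean of Free at Hour -1 and Hour 0), within participant and kinase, keeping the existing rule for a single available pre-dose sample. Use it in place of CFB and percent CFB, with the 90% CI attached to it.
3. If % Free has a reference other than the participant's own pre-dose mean, keep uncorrected TO and its CI alongside. If the reference is that mean, the two coincide and one table is enough.
4. State that the correction assumes a multiplicative offset. If assay validation shows an additive background, deal with that before taking the ratio.

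The cost is wording in two documents, using the same samples and data. The downside is the modest mid-range loss of precision shown above and reliance on the multiplicative assumption; keeping uncorrected TO where the two differ guards against both.

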#### 5.2.2. Analyses for Categorical Endpoints

For categorical or ordinal variables, number of subjects, numbers and percentages of subjects meeting the categorical criteria will be supplied in accordance with current Pfizer's data and reporting standards.

### 5.3. Methods to Manage Missing Data

For the analysis of safety endpoints, the sponsor data standard rules for imputation will be applied.

Methods to handle missing PK data are described below.

Concentrations Below the Limit of Quantification:

In all data presentations (except listings), concentrations below the limit of quantification (BLQ) will be set to zero. (In listings BLQ values will be reported as “<LLQ” where LLQ will be replaced with the value for the lower limit of quantification).

Deviations, Missing Concentrations and Anomalous Values:

In summary tables and plots of median profiles, statistics will be calculated having set concentrations to missing if 1 of the following cases is true:

1. A concentration has been collected as ND (ie, not done) or NS (ie, no sample),
2. A deviation in sampling time is of sufficient concern or a concentration has been flagged anomalous by the pharmacokineticist.

Note that summary statistics will not be presented at a particular time point if more than 50% of the data are missing.

Pharmacokinetic Parameters:

Actual PK sampling times will be used in the derivation of PK parameters. If a PK parameter cannot be derived from a subject's concentration data, the parameter will be coded as NC (ie, not calculated). (Note that NC values will not be generated beyond the day that a subject discontinues). In summary tables, statistics will be calculated by setting NC values to missing; and statistics will be presented for a particular dose with  $\geq 3$  evaluable measurements.

If an individual subject has a known biased estimate of a PK parameter (due for example to an unexpected event such as vomiting before all the compound is adequately absorbed from the gastrointestinal tract), this will be footnoted in summary tables and will not be included in the calculation of summary statistics or statistical analyses.

## **6. ANALYSES AND SUMMARIES**

### **6.1. Primary Endpoint(s)**

The primary analysis will be performed on the PD population (see [Section 4](#)).

The primary endpoint is TO of JAK3, BTK, ITK, RLK, TEC and BMX after a single dose of ritlecitinib. TO profiles, CFB and percent CFB in TO profiles of each kinase will be assessed graphically and summarized by dose and nominal timepoints using appropriate descriptive statistics as described in [Section 5.2.1](#).

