**Figure 1. Study Schema**

### **3. ENDPOINTS AND BASELINE VARIABLES: DEFINITIONS AND CONVENTIONS**

#### **3.1. Primary Endpoint(s)**

The primary endpoint in human PBMCs is TO of JAK3 BTK, ITK, RLK, TEC and BMX after a single dose of ritlecitinib. Target occupancy for each kinase at time  $t$  will be evaluated as follows:

$$\% \text{ Target Occupancy}_t = 100 \% - \% \text{ Free Target}_t$$

with  $TO_0$  as the baseline variable of target occupancy, which is the mean of the two pre-dose measurements at Hour -1 and Hour 0 on Day 1. If only one of the two pre-dose measurements is available,  $TO_0$  is the available pre-dose measurement. (see [Section 3.4](#)).

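### Percent change from baseline in target occupancy divides by a pre-dose occupancy that should be close to zero

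*SAP*

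**What the plan says.** SAP 3.1, like Protocol 9.3.1, defines occupancy (TO) of each kinase at time t as 100% minus the percentage of free target. TO_0 serves "as the baseline variable of target occupancy, which is the mean of the two pre-dose measurements at Hour -1 and Hour 0 on Day 1". SAP 3.4 repeats this and adds: "If only one of the two pre-dose measurements is available, the baseline will be defined as the available pre-dose measurement".

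For the primary endpoint SAP 6.1 plans three summaries: "TO profiles, CFB and percent CFB in TO profiles of each kinase will be assessed graphically and summarized by dose and nominal timepoints". Protocol 9.3.1 plans only one: "TO profiles will be assessed graphically and summarized by nominal timepoints using descriptive statistics".

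Under SAP 5.2.1 continuous data are summarised "using the number of subjects, mean, median, standard deviation, minimum, and maximum in accordance with current Pfizer's data and reporting standards". The same section adds: "For the summaries of TO and baseline corrected TO, the 90% CI for the mean will also be presented".

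Protocol 8.4.2.1 describes the assay: "An ATP-competitive probe will be used to pull-down kinases that are not covalently bound to PF-06651600".

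SAP 5.3 refers safety imputation to sponsor standards and then says "Methods to handle missing PK data are described below". It has no rule for TO.

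**The concern.** SAP 6.1 lists CFB and percent CFB as separate items, so percent CFB cannot simply mean a change in percentage points. The usual reading is a ratio with TO_0 as divisor. In healthy participants who have not yet been dosed, occupancy by the drug should be about zero. A ratio with such a divisor can be undefined, very large, or negative when occupancy has in fact risen.

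One of the three planned summaries of the primary endpoint is affected: 6 kinases x 2 doses x 6 post-dose times (1, 2, 4, 8, 24 and 48 hours in Protocol Table 2) = 72 summary cells, plus the matching plots. A reader of the report could take these figures for drug effect.

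**Working it through.** There is no planned figure to reproduce. The documents give no expected TO_0, no assay SD and no reference (100% level) for free target.

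**1. Is TO_0 near zero?** This is an inference.
- The assay counts kinase not bound by the drug, and both baseline samples precede the single dose.
- Known participation in a ritlecitinib trial within 30 days before dosing is excluded (Protocol 5.2, criterion 14).
- The drug half-life is about 2 hours (Protocol 2.2.4). Target half-lives are 2-3 hours for JAK3 and ITK and 12-24 hours for BTK (Protocol 2.1); none is given for RLK, TEC or BMX.
- Thirty days is 720 hours: 720/2 = 360 drug half-lives, and 720/24 = 30 BTK half-lives at the slow end. Carry-over is not expected for these kinases.

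**2. The formula.** The SAP does not write it out. The usual form is assumed:

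percent CFB = 100 x (TO_t - TO_0) / TO_0

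With TO_t = 90:

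| TO_0 | Absolute CFB (points) | Percent CFB |
|---|---|---|
| 20 | 70 | 350% |
| 5 | 85 | 1,700% |
| 1 | 89 | 8,900% |
| 0 | 90 | undefined |
| -2 | 92 | -4,600% |
| -5 | 95 | -1,900% |

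A negative baseline reverses the sign although occupancy rose.

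**3. What the reference for free target does.**
- *(a) The participant's own pre-dose mean.* TO_0 is exactly 0 by algebra. For example, free kinase of 95 and 105 gives TO of +5 and -5, mean 0. Percent CFB is undefined for everyone.
- *(b) A single pre-dose sample, or another reference with little background.* If Hour 0 is the reference, TO_0 = (100 - 100 x F(-1)/F(0))/2, where F is measured free kinase. At an assumed assay CV of 5%, TO_0 has an SD of about 3.6 points and half of its values are negative.
- *(c) A reference with background well above noise.* The ratio is stable, but the table shows the same 90% occupancy as 1,700% or 350% for an error-free background of 5% or 20%.

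**4. Size, by simulation.** All inputs except the 8 per arm and the two pre-dose samples are assumptions. The model is TO_0 ~ N(background, SD/√2) and TO_t ~ N(90, SD), with 200,000 arms of 8. Ranges are the 5th to 95th percentile of the arm statistic for percent CFB.

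| Background, SD (points) | Arm mean | Arm median |
|---|---|---|
| 0, 5 | about -20,000% to +20,000% | about -4,050% to +3,850% |
| 5, 5 | -5,600% to +9,300% | 980% to 2,610% |
| 5, 2 | 1,520% to 2,460% | 1,415% to 2,137% |
| 10, 5 | 679% to 1,566% | 625% to 1,092% |
| 20, 5 | 315% to 425% | 300% to 415% |

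- In the first row, mean absolute CFB lies between 86 and 94 points.
- The chance of a baseline at or below zero is Φ(-background/(SD/√2)). At background 0 it is 0.50, so 1 - 0.5^8 = 99.6% of arms contain at least one. At background 5, SD 5 it is Φ(-1.414) = 0.079, so 1 - 0.921^8 = 48% of arms do.
- With Hour 0 as reference, the arm median runs from about -3,940% to +3,950% at CV 5%, and from about -1,970% to +1,980% at CV 10%.
- Lower occupancy does not help. At background 0, SD 5, the median runs from -1,411% to 1,214% for a true TO of 30%, and from -2,744% to 2,520% for 60%.

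**5. An alternative relative measure.** Percent change in free kinase divides by a quantity near 100. Its arm mean stays between -93% and -87% at background 0, SD 5, and between -91% and -84% at background 20, SD 5.

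**The case against.** - **The formula is not written in the SAP.** True; the ratio is an assumption. It is the standard meaning, and no other reading explains why CFB is listed separately.
- **Case (a) fits the SAP poorly.** If TO_0 were 0 by construction, CFB would equal TO and a separate baseline variable would be pointless. This makes (a) less likely without excluding it, and cases (b) and (c) do not depend on it.
- **The background may be clearly non-zero.** In that case percent CFB is stable, as the last row of the simulation table shows. It would still measure mainly the background.
- **A rule may exist out of sight.** SAP 5.2.1 cites sponsor standards that cannot be seen, and SAP 3.3.1, 3.4 and 6.3.1 contain redactions. A rule there cannot be ruled out. However, setting non-positive baselines to missing would, at a true baseline of 0, drop about half the participants according to assay noise.
- **The SAP may add analyses.** Protocol 9 allows this, and absolute CFB is also absent from Protocol 9.3.1. The addition is therefore no breach; it only means that deletion removes nothing the protocol promised.
- **Little depends on it.** This stands. There is no hypothesis test (Protocol 9.5, SAP 5.1), and no visible decision uses percent CFB.

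**Conclusion.** The point holds, as a minor one. Under each reference considered for free target, percent CFB in TO is undefined, driven by noise, or mainly a reading of assay background. No visible rule covers a zero or negative TO_0: the rules in SAP 3.1 and 3.4 cover one missing sample, and the non-safety rules in SAP 5.3 concern PK.

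The conclusion rests on the usual formula and, for the instability, on a pre-dose occupancy that is small relative to assay noise. The simulated ranges are illustrations because their main inputs are not in the documents. The damage is confined to one set of descriptive tables and plots; TO and absolute CFB are sound.

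**What to change.** In SAP 6.1, delete percent CFB for TO and keep TO and absolute CFB, defined as TO_t - TO_0 in percentage points. If a relative measure is wanted, use percent change in free kinase from pre-dose. Where the reference is the participant's own pre-dose mean this equals minus TO and adds nothing, so it is optional.

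Two clarifications would help: SAP 3.1 should state the reference for percent free target, and SAP 5.2.1 should say what baseline corrected TO means.

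The cost is SAP wording only, with fewer tables and figures to produce. Sampling, assay and sample size do not change.
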